6.1.2.2. Overall Response Rate

Responses will be categorized as CR, PR, stable disease (SD), or PD. In addition, a response category of not evaluable (NE) is provided for situations in which there is inadequate information to otherwise categorize response status. A response category of no disease (ND) is included for situations in which there is no evidence of tumor either at baseline or on study.

The ORR using the IRC assessments will be presented with 95% CI by treatment groups. In the calculation of response rates, subjects who do not have sufficient baseline or on-study tumor assessment to characterize response will be included in the denominator.

6.1.2.3. Lymph Node Response Rate

LNR rate will be presented with 95% CI by treatment groups. Only subjects that have both baseline and ≥ 1 evaluable post-baseline SPD will be included for this analysis.

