9.3. Analysis Conventions

9.3.1. Analysis Sets

9.3.1.1. Intent-to-Treat Analysis Set

The ITT analysis set includes all subjects who receive ≥1 dose of any study treatment (high-dose idelalisib or standard-dose idelalisib). In the ITT analysis set, study drug assignment will be designated according to planned allocation in this study, regardless of whether subjects receive a different study therapy from that to which they were allocated.

This analysis set will be used in the analyses of subject characteristics and all the tumor control and patient well-being endpoints. Subjects in the ITT analysis set who do not have sufficient baseline or on-study tumor status information to be adequately assessed for response status will be included in the denominators in the calculation of response rates.

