9.4.2.2. Categorical Endpoints

Response rates, lymph node response rate, splenomegaly response rate, hemoglobin response rate, hepatomegaly response rate, ALC response rate, platelet response rate, hemoglobin response rate, and neutrophil response rate will be described. In the calculation of response rates, subjects who do not have sufficient baseline or on-study tumor assessment to characterize response will be included in the denominator. For all analyses, the corresponding 95% CIs will be presented.

The potential influence of subject baseline characteristics on response rates may be explored with multiple logistic regression modeling.

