3.1.2. Full Analysis Set

The full analysis set (FAS) includes all subjects in the ITT analysis set who receive ≥ 1 dose of IDELA, with treatment assignments designated according to randomization. Because all the subjects received correct treatment as randomized, this analysis set will be used for both the efficacy and safety analyses.

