3.5. Data Handling Conventions and Transformations

- By-subject listings will be created for important variables in each eCRF module, and sorted by subject number, visit, and time (if applicable).
- Summary tables for continuous variables will contain the following statistics: N (number in analysis set), n (number with data), mean, standard deviation (StD), median, Q1, Q3, minimum, and maximum. The same number of decimal places as in the raw data will be presented when reporting minimum and maximum, 1 more decimal place than in the raw data will be presented when reporting mean, median and 2 more decimal places than in the raw data will be presented when reporting StD.
- Summary tables for categorical variables for baseline and safety data will include: N, n, percentage. The tables for efficacy endpoints will include standard error, and 95% confidence intervals (CI) on the percentage, where appropriate. Unless otherwise indicated, 95% CIs for binary variables will be calculated using the binomial distribution. The denominator for the percentages will be the number of subjects in the specified analysis set at the same treatment or total as appropriate, unless otherwise specified. Missing data will be included as a row in tables where it is appropriate. All percentages will be presented as 1-decimal point, unless otherwise specified. Percent equal to 100 will be presented as 100% and percent will not be presented for zero frequencies.
- Data from all sites will be pooled for all analyses.

- Analyses will be based upon the observed data unless methods for handling missing data are specified.
- For Kaplan-Meier estimates, the 95% CIs will be calculated using the Greenwood's formula with (complementary) log-log transformation.

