6.1.2.4. Complete Response Rate

The same analyses as specified for ORR in Section 6.1.2.2 will be performed for the CR rate.

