6.1.3. Between-Study Comparisons

6.2. Changes From Protocol-Specified Efficacy Analyses

The per-protocol analysis set and the safety analysis set are no longer applicable. The FAS will be used for both efficacy and safety analyses.

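### The SAP computes lymph node response rate on evaluable subjects only, against the protocol's denominator rule and without declaring the change, so the reported rate can only be equal or higher

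*SAP*

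**What the plan says.** Protocol 9.4.2.2 (Categorical Endpoints) opens its list with "Response rates, lymph node response rate, splenomegaly response rate" and goes on to the other component responses. It then sets the denominator rule: "subjects who do not have sufficient baseline or on-study tumor assessment to characterize response will be included in the denominator". Protocol 9.3.1.1, on the set used for all tumor control endpoints, says of subjects with too little baseline or on-study tumor information that they "will be included in the denominators in the calculation of response rates". Protocol 3.1.1 defines LNR as a proportion of subjects and sets no evaluability condition.

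The SAP treats three neighbouring endpoints in two ways:

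- **6.1.2.2, ORR:** repeats the protocol's denominator rule.
- **6.1.2.3, LNR:** "Only subjects that have both baseline and ≥ 1 evaluable post-baseline SPD will be included for this analysis".
- **6.1.2.4, CR:** "The same analyses as specified for ORR in Section 6.1.2.2 will be performed for the CR rate".

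SAP 6.2, the place for changes from the protocol's efficacy analyses, says "The per-protocol analysis set and the safety analysis set are no longer applicable" and that the FAS will be used instead. It does not mention the LNR denominator. The FAS "includes all subjects in the ITT analysis set who receive ≥ 1 dose of IDELA", which carries no evaluability condition. SAP 3.5 sets the default: "The denominator for the percentages will be the number of subjects in the specified analysis set", unless a section says otherwise. Appendix 1 labels all five LNR tables (2.3.1 to 2.3.5) FAS.

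**The concern.** LNR is a proportion of subjects, so a subject with no measurement can be counted as a non-responder. The best percent change in SPD (SAP 6.1.2.6) is different, because it cannot be computed without a measurement; an evaluable-only basis is natural there.

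Missing SPD values are foreseeable and may be informative. The first scheduled on-study scan is at Week 8, so a subject who dies or leaves before any scan counts as a non-responder for ORR but drops out of LNR. Under Protocol 7.5.5 a time point is not evaluable if any index lesion is missing. SAP Appendix 2, footnote d, lets placebo-randomized subjects who enroll follow local imaging practice until idelalisib starts, so a usable baseline SPD is not assured in that group.

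LNR would then stand beside ORR, overall and in four 17p/p53 subgroup tables, on a smaller denominator that the table label does not show. The three treatment groups could also be affected to different degrees.

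SAP 6.1.2.7 has the same problem for spleen and liver response. Restricting these to subjects with the baseline abnormality follows their definitions. Dropping those without sufficient post-baseline assessment does not follow Protocol 9.4.2.2. This point makes no claim about the ALC and blood-count responses.

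**Working it through.** The documents give no planned LNR or expected number of unevaluable subjects, so there is no figure of the plan's own to reproduce. The check is of direction, then scale.

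**Direction.** Let N be the FAS subjects in a group, m those without a usable baseline and post-baseline SPD pair, and x the responders. A subject without the pair cannot show a decrease of at least 50%, so x is the same under both rules.

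- Protocol rule: x/N
- SAP rule: x/(N−m)
- Ratio: N/(N−m) = 1/(1−m/N) ≥ 1

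The two rates are equal only if m = 0 or x = 0.

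**Scale, fixing the all-FAS rate.** The first rate is 44/54 = 81.5%, the Phase 1 CLL figure in Protocol 1.3.5.2.1, used only for scale. The 60% rate and all values of m/N are assumptions.

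| m/N | Factor | Reported if x/N = 81.5% | Reported if x/N = 60% |
|---|---|---|---|
| 2% | 1/0.98 | 83.1% | 61.2% |
| 5% | 1/0.95 | 85.8% | 63.2% |
| 10% | 1/0.90 | 90.5% | 66.7% |
| 15% | 1/0.85 | 95.9% | 70.6% |

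**Scale, fixing the evaluable rate.** Take N = 90 and m = 9 with about 81.5% LNR among evaluable subjects. The SAP would report 66/81 = 81.5% (exact 95% CI 71.3 to 89.2). The protocol rule gives 66/90 = 73.3% (63.0 to 82.1). The factor is again 90/81 = 1.11.

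**Effect of one dropped subject.** x/(N−1) − x/N = (x/N)/(N−1). At x/N = 0.815:

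- N = 110 (planned Arm A, Protocol 9.5): 0.815/109 = 0.75 points.
- N = 50 (assumed Arm B group): 0.815/49 = 1.7 points.
- N = 30 (assumed Arm B group): 0.815/29 = 2.8 points.

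The protocol synopsis gives about 90 per arm for the primary study where Protocol 9.5 gives about 110. The choice does not alter the conclusion.

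**Integer examples with exact 95% CIs (x and m assumed).**

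| N | All FAS | Evaluable only, fewer missing | Evaluable only, more missing |
|---|---|---|---|
| 110 | 90/110 = 81.8% (73.3 to 88.5) | m = 5: 90/105 = 85.7% (77.5 to 91.8) | m = 11: 90/99 = 90.9% (83.4 to 95.8) |
| 40 (assumed) | 33/40 = 82.5% (67.2 to 92.7) | m = 2: 33/38 = 86.8% (71.9 to 95.6) | m = 4: 33/36 = 91.7% (77.5 to 98.2) |

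**The case against.** The strongest counter-argument is a narrow reading of the protocol. Section 9.4.2.2 lists response rates as an item separate from LNR, and Protocol 7.5 ties its own denominator rule to best overall response. The rule might therefore cover only ORR and CR, which is where the SAP keeps it. This reading is possible but weak. LNR is listed in the sentence just before the rule, in the same paragraph, and Protocol 9.3.1.1 states the rule for the set used for all tumor control endpoints.

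The SAP also states its restriction openly in the LNR section, and Protocol 9.3.2.3 leaves the open-label portion to a separate SAP. The SAP 3.5 default yields to a specific statement, so those two SAP sections do not conflict. The FAS label is also used for tables that are necessarily subsets, such as duration of response. All of that is fair. It shows no intent to hide the basis, but it does not supply the missing entry in SAP 6.2 or a reason for treating LNR differently from ORR and CR.

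A third objection is that subjects who entered after unblinding did not need measurable nodes. Someone with no index lesion cannot show a 50% decrease, and counting that person as a failure may mislead. This stands as a condition on the fix, although Protocol 7.5 keeps even no-disease subjects in tumor response denominators.

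It also stands that every figure for the size rests on assumed m, and that no hypothesis test depends on LNR.

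**Conclusion.** The concern holds. The SAP's denominator for LNR departs from the protocol's, SAP 6.2 does not say so, and within the FAS the departure can only leave the rate unchanged or raise it. The comparison is confined to the FAS because the protocol's ITT set and the SAP's FAS contain different subjects.

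The direction follows from the definitions. The size is unknown: it is zero if every FAS subject has a usable SPD pair and otherwise grows as 1/(1−m/N), about 11% in relative terms when one subject in ten has none. The consequence is limited to how descriptive LNR, spleen and liver response rates are read. It should be corrected, but it does not threaten the trial's other main results.

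**What to change.** - **SAP 6.1.2.3:** base the main LNR analysis on the FAS and count subjects without a usable baseline and post-baseline SPD pair as non-responders.
- **SAP 6.1.2.7:** do the same for spleen and liver response among subjects with the baseline abnormality who lack sufficient post-baseline assessment.
- **Sensitivity row:** keep the evaluable-only rate, labelled as such, with its denominator shown.
- **Subjects without nodal disease:** if those whom the IRC documents as having no index lesion at baseline are excluded from LNR in any group, say so in SAP 6.2. Report their number separately from subjects with missing measurements.
- **SAP 6.2:** record any other departure from Protocol 9.4.2.2 that is kept, with the reason.

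The cost is SAP wording, a denominator change in the table programs and one extra row. No new data are needed. The reported rates will be equal or slightly lower.

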6.1.2.4. Complete Response Rate

The same analyses as specified for ORR in Section 6.1.2.2 will be performed for the CR rate.

6.1.2.5. Time to Response and Duration of Response

TTR and DOR will be evaluated using IRC assessments based on subjects who achieve a CR or PR. Descriptive statistics will be provided for TTR. DOR will be summarized using Kaplan-Meier methods (medians, Q1, Q3, and corresponding 95% CIs) and the Kaplan-Meier curves will also be provided by treatment groups.

For the DOR analysis, data will be censored with the same manner as described in Section 6.1.2.1 for subjects who do not have disease progression, or who do not die on study, or start new anti-tumor therapy, or have ≥ 2 consecutive missing tumor assessments before disease progression or death.

6.1.2.6. Best Percent Change in Lymph Node Area

The best percent change in SPD from baseline during the study will be summarized using descriptive statistics. The summary is based on subjects with sufficient baseline and on-study tumor measurements for the SPD calculation per IRC. The best percent change from baseline in SPD is defined as the largest decrease in tumor size during the study. The baseline SPD will be the last value collected prior to the baseline reference date for efficacy endpoints. Note that for subjects who only have increases in tumor size from baseline, the smallest increase will be considered as the best change from baseline in SPD. Waterfall plots of best on-study percent change in SPD will be provided for each treatment group using IRC data.

6.1.2.7. Other Categorical Endpoints

Splenomegaly response rate, hepatomegaly response rate, ALC response rate, platelet response rate, hemoglobin response rate, and neutrophil response rate will be presented with 95% CIs. In the calculation of response rates, only subjects who have relevant abnormality, sufficient baseline and post-baseline assessments to characterize response will be included in the analysis.

The ALC, platelet, hemoglobin, and neutrophil responses will be listed with flags to indicate the use of any supportive care for corresponding hematologic lab parameters.

6.1.2.8. Overall Survival

OS will be described in the ITT analysis set using Kaplan-Meier methods by treatment group according to the original randomization in Study GS-US-312-0116. Median OS with Q1, Q3, and the Kaplan-Meier estimates of OS rate by every 6 months with corresponding 95% CIs will be presented. The Kaplan-Meier curve will also be plotted.

Data from surviving subjects will be censored at the last time that the subject was known to be alive on study or long term follow up.

Sensitivity analyses will be conducted by censoring OS on the first date of IDELA dosing for subjects in Arm B. OS will also be analyzed using the rank-preserving structural failure time (RPSFT) model {33006} to adjust for cross over effects.

6.1.2.9. Health-Related Quality of Life

The FACT-Leu questionnaire includes subscales for physical well-being (PWB, 7 items), social/family well-being (SWB, 7 items), emotional well-being (EWB, 6 items), functional well-being (FWB, 7 items), and additional concerns (Leukemia-Specific Subscale [LeuS], 17 items). The FACT-Leu scoring guide identifies those negatively stated items that must be reversed before being added to obtain subscale totals. Negatively stated items are reversed by subtracting the response from "4". After reversing proper items, all subscale items are summed to a total, which is the subscale score. For all FACT-Leu scales and symptom indices, the higher score is associated with the better quality of life. The scores in the following items need to be reversed according to the standard scoring guidelines:

- Physical well-being: all individual items
- Social/family well-being: none
- Emotional well-being: 5 individual items (except for GE2: "I am satisfied with how I am coping with my illness")
- Functional well-being: none
- Additional concerns: all individual items (except for C6: "I have a good appetite" and An7: "I am able to do my usual activities")

The subscale scores will be a summation of each individual item score. If $\leq 50\%$ of item scores are missing, the subscale score will be calculated by multiplying the sum of the item scores by the number of items in the subscale, then divided by the number of non-missing item scores. This imputes the missing scores by the mean of the non-missing scores within a subscale.

Prorated subscale score = [sum of item scores] × [N of items in subscale] / [N of items answered]

The following composite scores will be derived from the above subscale total scores:

- Trial Outcome Index (TOI, score range: 0-124) = PWB + FWB + LeuS
- FACT-G Total Score (score range: 0-108) = PWB + SWB + EWB + FWB
- FACT-Leu Total Score (score range: 0-176) = PWB + SWB + EWB + FWB + LeuS

The total scores will be set to missing if 20% or more of the included items are missing or any of the component subscales are missing. TOI scores are set to missing if any of the component subscales are missing.

As a baseline, the last value obtained prior to the baseline reference date for efficacy endpoints, as defined in Section 3.5.1, will be used. The mean and change from baseline in mean scores to each subsequent assessment will be summarized for the subscale and composite scores. The best change from baseline during the study, defined as the highest positive value among all post-baseline visits minus the baseline value, will also be summarized.

Each subject's FACT-Leu subscales (ie, PWB, EWB, SWB, and FWB) scores at each assessment will be compared to their baseline scores. The minimally important difference (MID) for these subscales is 3 points {26297}. An increase of at least 3 points will be required as a definition of symptom improvement. The cumulative distribution function (CDF) of best change from baseline will be provided. For the MID improvement comparison, subjects with baseline score > 55 will be excluded (ie, subjects with no room for improvement). Time to symptom response will be assessed by defining the first occurrence of symptom improvement as an event. Subjects who do not experience a symptom improvement compared to baseline will be censored at their last available FACT-Leu assessment time.

A data listing for each individual item, the subscale scores, and the composite scores will be presented for each subject at each time point.

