6.2.2. Visit 2 (Day 1) (Clinic Visit)

Subjects will be assessed to determine if they still meet eligibility criteria and can initiate study treatment. Study drug holds from primary study GS-US-312-0116 may continue as medically appropriate. The procedures outlined in Table 6-2 will be performed at Visit 2 (Day 1).

Table 6-2. Procedures and Assessments at Visit 2 (Day 1)

Assessment or Procedure	Explanation		
Pre-Dose Procedures and A	ssessments		
FACT-Leu	HRQL instrument (Appendix 2) to be administered before any other procedures are performed and before any study-related information is communicated to the subject		
EQ-5D	Health utility instrument (Appendix 4) to be administered after FACT-Leu but before any other procedures are performed and before any study-related information is communicated to the subject		
Adverse events	Recording of adverse events occurring since the initiation of the screening period		
Concomitant medications	Recording of concomitant medication use since the initiation of the screening period		
Performance status	Using Karnofsky performance status criteria (see Appendix 3)		
Oxygen saturation	To be assessed by pulse oximetry while subject is breathing room air		
Physical examination	Including weight, evidence of palpable lymphadenopathy, hepatomegaly, and/or splenomegaly		
β-НСС	For women of child-bearing potential only; serum β-HCG or urine dipstick pregnancy test must be negative prior to initial study treatment		
Hematology	Including hematocrit, hemoglobin, erythrocyte count; absolute counts of leukocytes, neutrophils, lymphocytes, monocytes, eosinophils, basophils, platelet count		
Serum chemistry	Including sodium, potassium, chloride, glucose, urea, creatinine, calcium, phosphorus, total protein, albumin, ALT, AST, ALP, GGT, total bilirubin, LDH, uric acid, cholesterol, triglycerides		
Idelalisib pharmacokinetics	Pre-dose collection of plasma sample for idelalisib pharmacokinetics (with recording of the date and actual clock time of blood collection)		
IWRS access	Access of IWRS to obtain study drug blister card number		
Study Therapy Administra	tion		
Study drug administration ^a	First dose of study drug to be administered to the subject (with recording of the date and actual clock time of the study drug administration)		
Post-Therapy Procedures a	Post-Therapy Procedures and Assessments		

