9.4.2.4. Health-Related Quality of Life and Performance Status

The FACT-Leu questionnaire data will be scored and processed according to the user manual. Missing items in a subscale will be imputed consistent with the user manual instructions. Data collected from the FACT-Leu instrument will not be reconciled with adverse event or laboratory data or with EQ-D5 findings.

As a baseline, the last value obtained prior to receiving the first idelalisib dose of 150 mg and 300 mg will be used, depending on the treatment group assigned.

The mean and change from baseline in mean scores to each subsequent assessment will be summarized for the FACT-Lym subscale and composite scores. The best change from baseline during the study, defined as the highest positive value among all post-baseline visits minus the baseline value, will also be summarized.

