 - Baseline for efficacy and safety endpoints will be the first dosing of IDELA, unless otherwise specified.
 - In the analysis, the Study GS-US-312-0117 portion will include all the data collected on or after the first dosing date of IDELA. The Study GS-US-312-0117 portion may include data collected in Study GS-US-312-0116, if a subject switches to open-label IDELA in Study GS-US-312-0116 while waiting for the protocol amendment.
- Placebo in GS-US-312-0116 + IDELA 150 mg BID in GS-US-312-0117:
 - Includes subjects who experience IRC confirmed PD in Arm B of Study GS-US-312-0116 and subsequently enroll into Study GS-US-312-0117 to receive IDELA 150 mg BID during the double-blind portion of the study
 - Referred to 'Placebo+R (PD)/IDELA' throughout this SAP and the TFLs
 - Baseline for efficacy and safety endpoints will be the first dosing of IDELA, unless otherwise specified.
 - In the analysis, the Study GS-US-312-0117 portion will include all the data collected on or after the enrollment date of Study GS-US-312-0117.

Efficacy and safety data collected during the primary and extension studies will be presented in the following 3 treatment groups:

- IDELA+R (PD, non-PD)/IDELA
 - Includes all subjects who are randomized to Arm A in Study GS-US-312-0116 (ie, all subjects in IDELA+R/IDELA and IDELA+R (PD)/IDELA)
 - For those in IDELA+R (PD)/IDELA, only data collected in Study GS-US-312-0116 (ie, while taking IDELA 150 mg BID) will be included. For those in IDELA+R/IDELA, all the data collected across Study GS-US-312-0116 and GS-US-312-0117 will be included. By this summary, the efficacy and safety profile of IDELA 150 mg BID can be explored for subjects randomized to Arm A in Study GS-US-312-0116.

- Baseline for efficacy endpoints will be the date of randomization in Study GS-US-312-0116.
- Baseline for safety endpoints will be the first dosing of IDELA 150 mg BID in Study GS-US-312-0116.
- Placebo+R/IDELA
- Placebo+R (PD)/IDELA

Due to the small sample size (N = 4) for the IDELA + R (PD)/IDELA group, data collected from this group in Study GS-US-312-0117 (ie, while taking IDELA 300 mg BID) will only be presented in listings.

Baseline for each data summary is described in Table 3-1.

	Baseline for Disposition Summary		Baseline for Efficacy Summary		Baseline for Safety Summary
Treatment Group	312-0116	312-0117	All endpoints except for OS	OS	All endpoints

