IDELA+R/IDELA	Date of randomization in Study GS-US-312-0116	Enrollment date of Study GS-US-312-0117	Date of randomization in Study GS-US-312-0116		First dosing date of IDELA in Study GS-US-312-0116
IDELA+R (PD)/IDELA	Date of randomization in Study GS-US-312-0116	Enrollment date of Study GS-US-312-0117	First dosing date of IDELA 300 mg BID in Study GS-US-312-0117		First dosing date of IDELA 300 mg BID in Study GS-US-312-0117
Placebo+R/IDELA	Not applicable	First dosing date of IDELA (Switching date to open-label IDELA)	First dosing date of IDELA (Switching date to open-label IDELA)	Date of randomization in Study GS-US-312-0116	First dosing date of IDELA (Switching date to open-label IDELA)
Placebo+R (PD)/IDELA	Not applicable	Enrollment date of Study GS-US-312-0117	First dosing date of IDELA 150 mg BID in Study GS-US-312-0117		First dosing date of IDELA 150 mg BID in Study GS-US-312-0117
IDELA+R(PD, non-PD)/ IDELA	Not applicable	Not applicable	Date of randomization in Study GS-US-312-0116		First dosing date of IDELA in Study GS-US-312-0116

Table 3-1.Baseline for Data Summaries by Treatment Group

Data from subjects who are randomized to Arm B in Study GS-US-312-0116 and never received IDELA in Study GS-US-312-0117 will be excluded from the analyses, unless otherwise specified.

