- Platelet response rate defined as the proportion of subjects with baseline thrombocytopenia (platelet count $< 100 \times 10^9/L$) who achieve an on-study platelet count $\ge 100 \times 10^9/L$ or demonstrate a $\ge 50\%$ increase in platelet count from baseline without need for exogenous growth factors. Platelet values within 4 weeks post-baseline or after 8 days post transfusion will be excluded from the platelet response rate evaluation.
- Hemoglobin response rate defined as the proportion of subjects with baseline anemia (hemoglobin < 110 g/L [11.0 g/dL]) who achieve an on-study hemoglobin ≥110 g/L (11.0 g/dL) or demonstrate a ≥ 50% increase in hemoglobin from baseline without red blood cell transfusions or need for exogenous growth factors. Hemoglobin values within 4 weeks post-baseline or after 4 weeks of receiving packed cell/whole blood transfusion or after 6 weeks receiving exogenous growth factors (e.g., Darbepoetin alfa) will be excluded for the hemoglobin response evaluation.
- Neutrophil response rate defined as the proportion of subjects with baseline neutropenia (absolute neutrophil count [ANC] ≤ 1.5 × 10⁹/L) who achieve an ANC > 1.5 × 10⁹/L or demonstrate a ≥ 50% increase in ANC from baseline without need for exogenous growth factors. ANC values within 4 weeks of post-baseline or after 2 weeks of receiving exogenous growth factors (e.g., Filgrastim, G-CSF, Lenograstim) or after 4 weeks of receiving Neulasta will be excluded for the neutrophil response evaluation.
- Overall Survival (OS) defined as the interval from the date of randomization in Study GS-US-312-0116 to death from any cause during the study or long term follow up
- Change from baseline in HRQL using FACT-Leu scores
- Changes from baseline in Karnofsky performance status
- Change from baseline in overall health and summary of single-item dimension scores as assessed using the EuroQoL Five-Dimension (EQ-5D) utility measure

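### Applied as a date comparison, the SAP's FACT-Leu baseline rule excludes the Day 1 pre-dose score in placebo-origin subjects whose first idelalisib dose is at 0117 Visit 2

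*SAP*

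**What the plan says.** SAP 6.1.1 lists "Change from baseline in HRQL using FACT-Leu scores" among the efficacy endpoints, so the efficacy reference date governs it. SAP 6.1.2.9 gives the baseline rule: "As a baseline, the last value obtained prior to the baseline reference date for efficacy endpoints, as defined in Section 3.5.1, will be used".

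SAP 3.5.1 sets the reference point by treatment group. For both placebo-origin groups the text reads "Baseline for efficacy and safety endpoints will be the first dosing of IDELA, unless otherwise specified". Table 3-1 states the same item as a date; for Placebo+R (PD)/IDELA the entry is "First dosing date of IDELA 150 mg BID in Study GS-US-312-0117". For the combined Arm A group the text reads "Baseline for efficacy endpoints will be the date of randomization in Study GS-US-312-0116".

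Protocol 9.4.2.4 has its own rule: "As a baseline, the last value obtained prior to receiving the first idelalisib dose of 150 mg and 300 mg will be used".

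On timing, Protocol Table 6-2 (Visit 2, Day 1) puts FACT-Leu first in the pre-dose block: "HRQL instrument (Appendix 2) to be administered before any other procedures are performed and before any study-related information is communicated to the subject". Later in the same table comes the entry "First dose of study drug to be administered to the subject". FACT-Leu and EQ-5D are absent from the screening table (Protocol Table 6-1). Their row in the schedule of procedures (Protocol Appendix 7, SAP Appendix 2) is blank at Visit 1 and first marked at Visit 2.

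SAP 6.2, on changes from the protocol's efficacy analyses, mentions only the analysis sets.

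**The concern.** A baseline rule that requires a value from before a given date works when the instrument is also given at screening. SAP 6.1.2.6 uses the same construction for the nodal SPD, and it works there because scans are taken in the screening period. FACT-Leu has no screening assessment in 0117. If its first 0117 administration falls on the reference date itself, the rule passes over the score that the visit schedule was built to capture before treatment.

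Every FACT-Leu result in SAP 6.1.2.9 depends on the baseline: change at each visit, best change, the cumulative distribution of best change, the 3-point improvement and time to symptom response. With an older 0116 score as baseline, any change in the subject's condition between that score and the start of idelalisib would be counted as change on idelalisib. With no baseline, the subject drops out of these summaries.

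**Working it through.** No figure in the plan is at issue, so the check compares dates. The SAP rule admits a score as baseline only if score date < reference date. The protocol rule admits it if it was obtained before the first dose.

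**Placebo+R (PD)/IDELA**
1. Reference date (SAP Table 3-1): first dosing date of 150 mg BID in 0117. Protocol Table 6-2 places the first dose at Visit 2, so this is Day 1.
2. First scheduled 0117 FACT-Leu: Visit 2, also Day 1, before the dose.
3. SAP test: Day 1 < Day 1 is false, so the score is excluded.
4. Protocol test: obtained before the dose is true, so the score is the baseline.
5. What remains under the SAP rule: no other 0117 score is scheduled before dosing. Protocol 2.1 says the two studies assess the same endpoints, so 0116 scores may exist. SAP 3.5.1 defines this group's 0117 portion as data from 0117 enrollment onward and does not say whether a 0116 score may serve as baseline. The result is an older score or a missing one.

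**The other groups**

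| Group | Efficacy reference date | Effect of the SAP rule |
|---|---|---|
| Placebo+R/IDELA, first dose at 0117 Visit 2 | First IDELA dosing date = Day 1 | Day 1 score excluded, as above |
| Placebo+R/IDELA, start delayed after Visit 2 (Protocol 5.1.2 allows this) | After Visit 2 | Visit 2 score precedes the date and is admissible |
| Placebo+R/IDELA, switched to IDELA while still in 0116 (SAP 3.5.1) | Falls in 0116 | Depends on the 0116 visit schedule; cannot be determined |
| IDELA+R (PD)/IDELA, 300 mg (N = 4) | First 300 mg dosing date in 0117 | Same logic, but SAP 3.5.1 puts these data in listings only |
| IDELA+R (PD, non-PD)/IDELA (all Arm A) | Randomization in 0116 | Depends on the 0116 visit schedule; cannot be determined |

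**Number affected.** SAP 1.3 gives 161 enrolled and SAP 3.5.1 gives 4 in the 300 mg group. The split of the other 161 − 4 = 157 is not stated, so the affected subjects cannot be counted.

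**Age of a substituted score.** Protocol 4.2.1 allows up to 12 weeks (12 × 7 = 84 days) between stopping 0116 treatment and starting 0117 therapy for entry to the blinded portion. That interval does not start at the last 0116 questionnaire, whose timing is not given.

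**The case against.** The strongest reply is that the rule defers to SAP 3.5.1, whose bullets for the placebo-origin groups name an event, the first dosing, rather than a date. Read that way, *prior to* means pre-dose, the Day 1 questionnaire is the baseline, and the SAP agrees with the protocol. This may well be what was meant. It does not settle the matter: the operative sentence in 6.1.2.9 speaks of a reference date, and Table 3-1 gives dosing dates. Protocol Table 6-2 asks for clock times for dosing and pharmacokinetic samples but not for the questionnaires, so a programmer would naturally compare dates.

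It is also fair to say that the stakes are limited. SAP 3.5.2 makes the analyses descriptive, with no formal comparison between groups.

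Three stronger readings are tempting and are not supported:
- *The Day 1 score could itself set the best change or count as a 3-point improvement.* Nothing classes it as post-baseline. The windows in SAP Table 3-2 apply to data after unblinding where the nominal visit no longer fits, and Week 0 there is a one-day window of its own. The score's status is left unstated, which is a reason to state it.
- *Arm A has no baseline.* That would need the first 0116 questionnaire to fall on the day of randomization, and the 0116 schedule is not in these documents.
- *EQ-5D and Karnofsky fail in the same way.* SAP 6.1.2.10 and 6.1.2.11 contain no such date rule. EQ-5D shares the FACT-Leu schedule, so it would be exposed if the rule were carried over. Karnofsky is also recorded at screening, so it has a 0117 value before Day 1.

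**Conclusion.** The rule is wrong as written and should be corrected. Applied as a date comparison, it excludes the only scheduled 0117 pre-treatment FACT-Leu score for Placebo+R (PD)/IDELA, and for Placebo+R/IDELA subjects whose first idelalisib dose is at 0117 Visit 2. This departs from Protocol 9.4.2.4, and SAP 6.2 does not record the departure.

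The conclusion assumes that first dosing takes place at Visit 2 as scheduled and that *prior to* a date excludes that date. The damage is an outdated or a missing baseline; the documents do not say which, nor give its size. A reader might infer that the substituted score would be well over four weeks old, but the 12-week entry limit does not measure the age of a questionnaire and gives no such figure. The conclusion does not extend to Arm A or to subjects who switched to idelalisib within 0116, for whom the effect cannot be determined.

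**What to change.** In SAP 6.1.2.9, define the FACT-Leu baseline as the last non-missing assessment on or before the efficacy reference date and before the first idelalisib dose. Add that the Day 1 pre-dose questionnaire is the baseline and is not a post-baseline value. Put the same sentence in 6.1.2.11 for EQ-5D, which is collected on the same schedule and has no baseline rule of its own.

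List in SAP 6.2 any difference from Protocol 9.4.2.4 that remains. One example is the use of 0116 randomization rather than first dose as the reference for Arm A.

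The cost is a sentence in each of two sections and an entry in 6.2. No new data are needed, because the Day 1 questionnaires are already scheduled.
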